8.5.5.6 Number of Days in the Hospital

The date of each hospital admission and discharge will be collected for each patient. The number of days when patients are in hospital during the first 28 Days of the study will be summarized by treatment group and compared between the 2 treatment groups using an analysis of variance model, which includes treatment group in the model, which includes treatment group as the fixed effect in the model.

Two sets of analyses will be conducted. The first analysis is to assess patient benefit; the number of days in the hospital will be defined as 28 if the patient dies due to COVID-19 (composite strategy). The second analysis is to assess healthcare systems benefit; the number of days in the hospital before the patient's death will be used in the analysis (while alive strategy).

8.5.5.7 Number of Days in the Hospital

The analysis will be the same as the number of days in the hospital

8.6 Tertiary Endpoint Analysis

8.6.1 Change in Imputed PaO₂/FiO₂ Ratio

SpO₂ and FiO₂ will be examined at each scheduled time point. Worst value within the previous 24 hours at each scheduled time point will also be recorded. Conversion from SpO₂ to PaO₂ will follow [Table 3](#).

Table 3 Look up table for conversion SpO₂ to PaO₂

Measured SpO ₂ (%)	Imputed PaO ₂ (mmHg)
100*	167*§
99*	132*
98*	104*

97*	91*
96	82
95	76
94	71
93	67
92	64
91	61
90	59
89	57
88	55
87	53
86	51
85	50
84	49
83	47
82	46
81	45
80	44
79	43
78	42
77	42
76	41
75	40
74	39
73	39
72	38
71	37
70	37
69	37

* Generally considered unreliable on the basis of the sigmoidal shape of the hemoglobin-oxygen dissociation curve

§ Based on SpO₂ 99.5%.

Mean changes from baseline to each post-baseline visit and time point will be summarized by treatment groups for both at visit imputed PaO₂/FiO₂ value and worst value within the previous 24 hours of the visit imputed PaO₂/FiO₂ value.

Change from baseline over time in the imputed PaO₂/FiO₂ will be analyzed using a mixed effect model repeat measurement (MMRM) model with an unstructured covariance structure (if model is estimable). The analysis model will include Baseline value of the endpoint as a covariate, study day and treatment as fixed effect, study day by treatment as interaction, and subjects as random effect. Point estimates, 95% CIs and p-values for the difference between the Auxora treated patients and local standard care group at each scheduled time point will be obtained.

Similar analysis to the above analysis will be conducted for the change from baseline over time in the imputed PaO₂/FiO₂ endpoint using the last observation carried forward method as the missing value imputation method.

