8 VISITS AND STUDY SPECIFIC ASSESSMENTS

8.1 Screening

The PI or designee must provide informed consent to the patient, or LAR, allowing the patient or LAR adequate time to consider, ask questions and receive answers, prior to agreeing to participate.

• Record the time of the patient or LAR provides informed consent

After informed consent is obtained, the following procedures are to be performed:

- Record Vital Signs
- Record Weight: may use weight obtained as part of standard of care
- Record results of Influenza A, B and Respiratory Panel if performed as local standard of care
- Record results of Sars-CoV-2 testing
- Record results of CXR or CT scan documenting a pulmonary infiltrate
- Record the lowest SpO₂ in the previous 24 hours and the time it was performed. The FiO₂ at the time of the SpO₂ measurement will also be recorded
- Record the SpO₂ and FiO₂ at the time closest to the Screening assessment
- Complete and record results of pregnancy test for women of child-bearing potential
- Record ABG and time drawn if performed as part of standard of care
- Complete Daily Assessment Ordinal Scale

If the patient satisfies all of the inclusion criteria and none of the exclusion criteria, proceed to baseline assessment.

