8.1.4 Derived Variables

8.1.4.1 Definition(s) of Baseline(s)

Unless otherwise specified, the baseline values are the last available assessment before or at the SFISD. If multiple measurements are recorded on the same day, the last measurement recorded prior to the dose of study medication will be used as the baseline value. If these multiple measurements occur at the same time or time is not available, then the average of these measurements (for continuous data) or the worst among these measurements (for categorical data) will be considered as the baseline value. **Baseline imputed PaO₂/FiO₂ is the worst value in the 24 hours before screening.**

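### Change in at-visit PaO₂/FiO₂ is measured from a worst-in-24-hours baseline, so the within-arm mean changes for that series are not like-for-like

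*SAP*

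**What the plan says.** SAP 8.1.4.1 opens with a general rule: "Unless otherwise specified, the baseline values are the last available assessment before or at the SFISD". It then makes an exception for one variable: "Baseline imputed PaO₂/FiO₂ is the worst value in the 24 hours before screening".

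SAP 8.6.1 applies change from baseline to two post-baseline series. One is the reading at the visit. For the other, "Worst value within the previous 24 hours at each scheduled time point will also be recorded". The summary sentence covers both ("Mean changes from baseline to each post-baseline visit and time point will be summarized by treatment groups for both at visit imputed" PaO₂/FiO₂ and the worst value). No separate baseline is given for either series. The mixed model takes the baseline value of the endpoint as a covariate, and the section does not say which of the two series the model analyses.

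Protocol 8.1 collects two screening pairs. The first instruction is "Record the lowest SpO₂ in the previous 24 hours and the time it was performed", with the FiO₂ at that moment. The second is "Record the SpO₂ and FiO₂ at the time closest to the Screening assessment". Protocol 8.4 adds a further SpO₂/FiO₂ reading before the first infusion, but only if more than 6 hours have passed since randomization. Protocol 8.5 to 8.10 record the same two kinds of reading at each later inpatient assessment.

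**The concern.** The lowest of several readings lies below a typical reading from the same patient. If the baseline is a window minimum and the follow-up value is a single reading, the difference is positive on average even when nothing has changed. The offset is then carried in every at-visit mean change that SAP 8.6.1 reports, in both arms.

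Within-arm mean change is a stated output of the section, and readers tend to take it as recovery of oxygenation. The mismatch is also avoidable, because a point-in-time screening pair is already on the case report form and the general baseline rule would have led to a point-in-time value.

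**Working it through.** The documents give no SD, expected change or power figure for PaO₂/FiO₂, so there is no stated figure to reproduce. The check has four parts.

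**1. Which comparison is matched**

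| Series (SAP 8.6.1) | Follow-up value | Baseline (SAP 8.1.4.1) | Matched? |
|---|---|---|---|
| At visit | single reading | worst in 24 h | no |
| Worst in previous 24 h | worst in 24 h | worst in 24 h | yes |

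**2. Illustration from the protocol's own table.** In Appendix 1 at FiO₂ 0.5, SpO₂ 0.90 gives 117, 0.93 gives 134 and 0.95 gives 151. A patient on unchanged oxygen with a 24-hour low of 90% and an at-visit reading of 93% to 95% is recorded as gaining 134 − 117 = 17 to 151 − 117 = 34 mmHg.

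**3. Expected offset with no true change.** Take k readings in the window, each normal with within-patient SD s. Then offset = E(single reading) − E(minimum of k) = d(k) × s, where d(3) = 0.85 and d(6) = 1.27. If the readings share a common correlation r, the offset is d(k) × s × √(1 − r). At r = 0.8 the factor is √0.2 = 0.447, so the multipliers become 0.38 and 0.57. The values of k, s and r are assumptions; none is in the documents.

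| Offset (mmHg) | s = 10 | s = 20 | s = 30 |
|---|---|---|---|
| k = 3, r = 0 | 8.5 | 17.0 | 25.5 |
| k = 6, r = 0 | 12.7 | 25.4 | 38.1 |
| k = 3, r = 0.8 | 3.8 | 7.6 | 11.4 |
| k = 6, r = 0.8 | 5.7 | 11.4 | 17.1 |

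A two-arm simulation with no change and no treatment effect (160 per arm, k = 6, independent readings, 4,000 runs, s = 10, 20 and 30) gave these results:
- At-visit minus worst baseline: +12.7, +25.3 and +38.0 mmHg.
- At-visit minus the screening reading: 0.0 throughout.
- Worst minus worst: 0.0 throughout.
- Arm difference in the as-written change: 0.02, −0.03 and 0.0 mmHg.

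**4. When the direction can reverse.** The form captures the lowest SpO₂ with its FiO₂, which need not be the lowest ratio. By Appendix 1, SpO₂ 0.88 on FiO₂ 0.36 gives 153. After oxygen is raised, SpO₂ 0.94 on FiO₂ 0.6 gives 118. If the baseline comes from the lowest-SpO₂ pair and the patient then stays at 118, the recorded change is 118 − 153 = −35 mmHg. If the baseline is the lower of the two recorded ratios, it cannot exceed the Screening ratio, but it is not then a minimum of 3 to 6 ratios.

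**The case against.** The strongest reply is that no inferential result is affected, and that stands. The confidence intervals and p-values in SAP 8.6.1 are for the difference between arms. Allocation is randomized, so the offset is expected to be equal in both. In the mixed model the baseline is also a covariate, so subtracting it from the outcome changes its own coefficient by 1 and leaves the treatment estimate as it was. A reader might infer that the choice of baseline favours Auxora; the documents do not support that.

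A reader might also infer that a mismatched covariate costs precision. Under independent readings the opposite holds. The minimum of 6 has variance 0.42 s². With an assumed between-patient SD of 30 and s = 25, a single reading correlates with a later at-visit value at 900/(900 + 625) = 0.59. The minimum of 6 correlates at 900/√[(900 + 0.42 × 625)(900 + 625)] = 0.68. Only under strong serial correlation is the single reading better, and then slightly (first-order autoregressive 0.8: 0.697 against 0.690; 0.9: 0.809 against 0.783).

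It is also fair to say that the baseline is openly pre-specified, that it fits the 24-hour window of inclusion criterion 3, and that one of the two series is already matched. The phrase about the baseline value of the endpoint could be read as implying a baseline specific to each series, but it does not displace the explicit definition in SAP 8.1.4.1. What remains is a descriptive within-arm summary whose meaning depends on an unstated pairing.

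**Conclusion.** The point holds for one output: the within-arm mean changes of the at-visit series, for a tertiary endpoint outside the multiplicity scheme. If worst means the lowest ratio, these changes include an apparent gain of about 0.85 to 1.27 within-patient SD for 3 to 6 independent readings, and less with correlated readings. Any mmHg figure rests on an assumed SD, number of readings and correlation, so none should be read as an estimate for this trial.

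A reader might conclude that both arms are certain to show improvement. The documents do not support that either. If worst is derived from the lowest-SpO₂ pair, the offset can shrink or reverse in patients whose FiO₂ was raised before screening.

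The worst-in-24-hours series is matched, apart from regression to the mean that comes from selecting patients at a ratio of 200 or less. The primary and key secondary tests are untouched. This is a minor clarification, worth making because the output is planned and the matched reading is already collected.

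**What to change.** Add one sentence to SAP 8.6.1, with a cross-reference in 8.1.4.1:

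- For the at-visit series, take baseline as the ratio from the pair recorded "at the time closest to the Screening assessment" (Protocol 8.1), or from the pre-infusion pair where one is recorded. Protocol 8.4 requires the latter only after a delay of more than 6 hours, so the Screening pair is the option with uniform timing.
- For the worst-value series, and for the population and stratum definitions, keep the worst-in-24-hours ratio.
- State whether worst means the lower of the recorded ratios or the ratio at the lowest SpO₂.
- State which series and which baseline the mixed model and its last-observation-carried-forward version use. The worst value may stay in the model as an additional covariate.

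The cost is one SAP sentence and one derived variable. No new data are needed.

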8.7 Safety Analysis

The safety evaluation will be purely descriptive using descriptive statistics (N, mean, SD, median minimum and maximum) or frequency tables where appropriate using Safety Analysis Set, unless otherwise specified. No imputation will be made in case of missing values.

8.7.1 Study Medication Exposure

Number of doses of double-blind study medication will be summarized in table and presented in data listing for the safety population.

8.7.2 Adverse Events

Adverse events will be coded using MedDRA dictionary. If an incomplete or missing onset date was collected for an AE, the imputation method of missing data specified in Section 8.1.4.4 will be applied. Treatment-emergent AEs (TEAEs) are defined as AEs that started or worsened in severity on or after the SFISD.

The relationship to study treatment for each AE will be classified as ‘Unrelated’, ‘Unlikely’, ‘Possible’, ‘Probable’, ‘Definite’. AEs classified as ‘Possible,’ ‘Probable’ and Definite will be analyzed as ‘Related’ in the AE summaries. Data listings, patient narratives, etc. will present the relationship to study treatment as collected on the CRF.

8.7.2.1 Tabulations of TEAEs

The frequency and incidence of TEAEs will be summarized by System Organ Class (SOC) and Preferred Term (PT) by treatment and then by overall treatment. The actual version of the MedDRA coding dictionary used will be noted in the clinical study report. The SOC is sorted by alphabetic order; then within SOC, PT is sorted by descending counts under Auxora column, then descending counts under Placebo column, then alphabetic order for PTs with the same count.

Each of the summaries will be done at the subject level. Multiple occurrences of the same event within a subject will be counted once in the summaries by System Organ Class and PT.

All AEs for each subject, including multiple occurrences of the same event, will be presented in full in a comprehensive listing including subject number, treatment, severity, seriousness, action taken, outcome, relationship to treatment, onset/stop date and duration.

The data listings for serious TEAE and TEAE leading to discontinuation of study treatment will be generated as well.

8.7.2.2 Adverse Event Overview

An overview of AEs will be presented by the actual treatment received overall and consisting of the number and percentage of patients experiencing at least one event for the following AE categories:

- Any TEAEs
- TEAEs related to study treatment
- Serious TEAEs
- Serious TEAEs related to study treatment
- TEAEs leading to discontinuation of study treatment
- TEAEs leading to death

8.7.2.3 Adverse Event by SOC and PT

The following summaries of AEs will be generated:

- Incidence of TEAEs
- Incidence of TEAEs related to study treatment
- Incidence of serious TEAEs
- Incidence of serious TEAEs related to study treatment
- Incidence of TEAEs leading to discontinuation of study treatment
- Incidence of TEAEs leading to death
- Incidence of severe TEAEs

8.7.3 Additional Safety Assessments

8.7.3.1 Vital Signs

Vital signs will include temperature, systolic and diastolic blood pressure, respiratory rate (breaths per minute), heart rate (beats per minute).

Vital signs will be examined at each scheduled visit and time point. Clinically-significant, treatment-emergent findings will be reported as AEs.

In addition, vital signs results will be flagged as potentially clinically significant (PCS) if they meet the criteria which are defined below.

- Pulse rate >140 bpm.
- Pulse rate <45 bpm.

- Diastolic blood pressure >100 mmHg.
- Systolic blood pressure >155 mmHg.
- Systolic blood pressure <60 mmHg.
- Body temperature $\geq39^{\circ}\text{C}$.

The number and percent of patients meeting each PCS criterion at each scheduled visit and time point will be summarized by the actual treatment and then by the overall treatment.

8.7.3.2 Laboratory Analyses

CBC with Differential, Serum Chemistries, Ferritin, C-reactive protein, Procalcitonin and D-Dimer will be performed.

Laboratory values by visit will be summarized as boxplots. The lower and upper reference range values for lab tests will be used to grade the lab results to low, normal and high categories. Shift tables will display:

1. Shift from baseline category to the worst category;
2. Shift from baseline category to the last category.

8.8 Other Analyses

8.8.1 Other Variables and/or Parameters

Biomarkers will be measured at baseline and with subsequent assessments at various timepoints up to 240 hours. Log-transformation will be applied when necessary. Change from baseline over time will be analyzed using a mixed effect model repeat measurement (MMRM) model with an unstructured covariance structure (if model is estimable). The analysis model will include Baseline value of the endpoint as a covariate, study day and treatment as fixed effect, study day by treatment as interaction, and subjects as random effect. Point estimates, 95% CIs and p-values for the difference between the Auxora treated patients and local standard care group at each scheduled time points will be obtained.

8.8.2 Subgroup Analyses

Subgroup analyses will be performed to explore how time to recovery through Day 60 visit and mortality at Day 60 visit are influenced by baseline variables and to evaluate the treatment effect at different levels of each of these variables. The Kaplan-Meier analysis, Cox model and CMH test will be performed by subgroup levels of the baseline variables listed below:

- Age ($<65, \geq65$)
- Baseline CRF calculated imputed $\text{PaO}_2/\text{FiO}_2$ ($\leq100, 101-200, \geq201$)

- Race (White, Black, Asian, Other).
- Gender (Male, Female)
- BMI ($<30, \geq 30$)
- Remdesivir (being already administered at randomization, administration started after randomization, never administered)
- Dexamethasone (being already administered at randomization, administration started after randomization, never administered)
- Remdesivir and Dexamethasone (being already administered together at randomization or administered together starting after randomization)
- Convalescent plasma (being administered at randomization, administration started after randomization, never administered)

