10.8.10 Subgroup and Exploratory Analyses

Subgroup analyses will be performed to explore how time to recovery is influenced by baseline variables and to evaluate the treatment effect at different levels of each of these variables. The Kaplan-Meier analysis and Cox model will be performed by subgroup levels of the baseline variables listed below:

- Age $(<75, \ge 75)$
- Baseline PaO_2/FiO_2 (>200, ≤100, 101-200, 201-300, all randomized patients)
- Receiving high flow oxygenation versus low flow oxygenation at randomization
- Race (White, Black, Asian, Other).
- Gender (Male, Female)
- BMI ($<30, \ge 30$)
- Remdesivir (being already administered at randomization, administration started after randomization, never administered)
- Dexamethasone (being already administered at randomization, administration started after randomization, never administered)
- Remdesivir and Dexamethasone (being already administered together at randomization or administered together starting after randomization)
- Convalescent plasma (being administered at randomization, administration started after randomization, never administered)

Additional subgroups may also be further described in the Statistical Analysis Plan.

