4 SAMPLE SIZE

In the initial design of Part 2 of the study, 320 patients in the baseline imputed $\text{PaO}_2/\text{FiO}_2 \leq 200$ subgroup and 80 patients in the baseline imputed $\text{PaO}_2/\text{FiO}_2 > 200$ subgroup were to have been randomized. A constant recovery rate ratio of 1.43 was assumed for patients receiving Auxora compared to Placebo in both subgroups. In order to provide power of approximate 90% to detect a difference in the recovery rate ratio of approximately 1.43 by a stratified 2-sided log-rank test at an overall 0.05 alpha level, given the 1:1 randomization, it was determined that the study would require 330 recovery events. With the study length of 30 days, the assessment of time to recovery required a sample size of 400 patients.

The enrollment of patients in the subgroup with a baseline imputed $\text{PaO}_2/\text{FiO}_2 > 200$ was stopped early because a blinded analysis of the data from the first 26 patients in the subgroup randomized into the study showed a low rate of mechanical ventilation or death. This finding was consistent with Part 1 of the study where no patients with a baseline imputed $\text{PaO}_2/\text{FiO}_2 > 200$ required mechanical ventilation or died.

The Part 2 study sample size was then reevaluated given that the primary endpoint would focus on the subgroup of patients with a baseline imputed $\text{PaO}_2/\text{FiO}_2 \leq 200$. A two group log-rank test with a 0.05 two-sided significance level would have 90% power to detect a difference in the recovery rate ratio of approximately 1.49 in the 320 patients with a baseline imputed $\text{PaO}_2/\text{FiO}_2 \leq 200$ who were randomized 1:1 to Auxora or Placebo.

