8.1.2 Significance Level and Confidence Interval

The statistical tests will be performed as two-sided with significance level of 5%. The confidence intervals will be determined with a confidence level of 95%.

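### The subgroup plan analyses treatment within each level but includes no interaction or homogeneity test, so it never formally assesses whether the effect differs between levels

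*SAP*

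**What the plan says.** SAP 8.8.2 has two aims: to explore how time to recovery and Day 60 mortality depend on baseline variables, and "to evaluate the treatment effect at different levels of each of these variables". The method is a single sentence: "The Kaplan-Meier analysis, Cox model and CMH test will be performed by subgroup levels of the baseline variables listed below". Nine factors follow: age, baseline imputed PaO2/FiO2, race, gender, BMI, remdesivir, dexamethasone, the two drugs together, and convalescent plasma. The last four include categories for treatment begun after randomization.

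Protocol 10.8.10 takes the same approach for recovery: "The Kaplan-Meier analysis and Cox model will be performed by subgroup levels of the baseline variables listed below".

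Neither section contains a treatment-by-factor term, a test of homogeneity, or guidance on reading differences between levels. The only interaction in the SAP is study day by treatment, in the repeated-measures models of 8.6.1 and 8.8.1, which is a different matter. SAP 8.1.2 sets a general two-sided 5% level. The multiplicity control in 8.4.2 and 8.5.2 covers only the primary and key secondary tests.

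**The concern.** An analysis inside one level asks whether there is an effect in that level. Whether the effect differs between levels is another question, and it needs a direct comparison of the two estimates. A significant result in one level and a non-significant one in the other is not that comparison, because each level has only part of the events and so much less power than the whole trial.

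With no interaction test planned, the by-level results are the only subgroup evidence the report will contain. A reader who sets one level's result against another's could conclude that the drug works only in, say, younger or heavier patients when the effect is the same throughout. The stake is the interpretation of exploratory results, not the trial's main conclusion.

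**Working it through.** **Inputs**
- Initial design (SAP 4): ratio 1.43, 90% power, two-sided 0.05, 1:1 allocation; "it was determined that the study would require 330 recovery events", in 400 patients.
- Current design (SAP 4): a log-rank test that "would have 90% power to detect a difference in the recovery rate ratio of approximately 1.49 in the 320 patients".
- Events (SAP Table 4): 266 in the 320-patient row and 415 in the 500-patient row.
- Shares of patients per level: not in the documents. The splits below are assumptions, shown as a range.

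**The plan's own figures**, with Schoenfeld's formula
- Events = 4(1.96 + 1.2816)² / (ln 1.43)² = 329, against 330 stated.
- Power = Φ(√266/2 × ln 1.49 − 1.96) = 0.902, against 90% stated. With 320 × 330/400 = 264 events it is 0.900.

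Both reproduce, so the same formula is used within levels.

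**Discordance under a uniform effect.** A level with share f of the events has power p = Φ(√(266f)/2 × ln 1.49 − 1.96). The levels of a factor contain different patients, so their tests are independent. The chance that exactly one of two is significant is p₁(1 − p₂) + p₂(1 − p₁).

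| Assumed split | Power in each level | Exactly one significant |
|---|---|---|
| 50:50 | 0.633, 0.633 | 2 × 0.633 × 0.367 = 0.465 |
| 70:30 | 0.777, 0.429 | 0.777 × 0.571 + 0.429 × 0.223 = 0.539 |
| 80:20 | 0.829, 0.307 | 0.829 × 0.693 + 0.307 × 0.171 = 0.627 |

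**Sensitivity**
- Ratio 1.43, 266 events: 50% (50:50) to 62% (80:20). Ratio 1.34: 48% to 54%.
- 415 events, 50:50: at ratio 1.49, power is 0.819 per level and discordance 2 × 0.819 × 0.181 = 0.30; at 1.34, power is 0.559 and discordance 0.49.
- Three equal levels (266 events, ratio 1.49): mixed results 75%. Four equal levels: 82%.
- PaO2/FiO2 ≥201, capped at 26 patients: 26 × 0.825 = 21 events gives about 15% power at 1.49.
- Mortality: the documents give no rates. Assuming 160 per arm, a 50:50 split and 20% v 12%, power is 28% per level and discordance 40%. Over 15% v 9% to 30% v 18%, discordance is 34% to 49%.

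**What an interaction test would do**
- False flags: 5% per test by construction; 0.049 to 0.051 in simulation with 264 events split 50:50.
- Across tests: five factors and two endpoints make 10 tests. If independent, the chance of at least one false flag is 1 − 0.95¹⁰ = 0.40. With all nine factors it is 1 − 0.95¹⁸ = 0.60.
- Power: with 264 events split 50:50, the difference in log ratios has standard error √(16/264) = 0.246. For true ratios of 1.49 and 1.00, power is Φ(0.399/0.246 − 1.96) = 0.37. Power of 80% needs the two ratios to differ by a factor of about 1.99.

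**The case against.** A reader might infer that the plan judges subgroup effects by comparing p-values. The documents do not say so. SAP 8.8.2 is framed as exploration, the protocol puts the analysis under an exploratory heading, and no significance or decision rule is given. Where the SAP wants p-values from a model it asks for them, as in 8.6.1 and 8.8.1; 8.8.2 does not. SAP 8.4.4 uses the Cox model to estimate a ratio with its confidence interval, and such estimates can be compared by eye. Only the CMH analysis is called a test.

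A reader might also infer that the section cannot meet its own aims. That is too strong, because by-level estimates do describe the effect at each level. What they leave out is a formal assessment of whether those effects differ.

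Three further points stand:
- The discordance percentages become misleading conclusions only if someone compares significance across levels, which the plan does not instruct.
- SAP 9.1 says the updated re-estimation rule used 500 patients. It does not say whether the increase took place, so the lower 415-event figures belong beside the 266-event ones.
- An interaction test on every listed factor would be wrong. For four of the nine, some categories are defined by treatment started after randomization, which the study drug may itself influence. The combined remdesivir and dexamethasone entry also has no category for patients who never received both.

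The gap remains after all this: no interaction or homogeneity test is planned, and nothing tells the reader how to treat differences between levels.

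**Conclusion.** The point holds as an omission from an exploratory section. If within-level significance is compared, a uniform effect at the design ratio of 1.49 with 266 events would look discordant in about 47% to 63% of two-level factors for recovery. At 415 events and an even split, the figure is about 30% at ratio 1.49 and 49% at 1.34. These figures rest on assumed subgroup splits, a constant ratio in every level and the same share of patients recovering in each. The mortality figures also rest on assumed death rates.

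The primary and key secondary tests, the sample size and the type I error control are untouched. It would be wrong to read this as a threat to the main result, or as evidence that a false subgroup claim is planned. It is a cheap improvement.

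**What to change.** Amend SAP 8.8.2 as follows:
- **Five true baseline factors** (age, baseline imputed PaO2/FiO2, race, gender, BMI): add one treatment-by-factor interaction test per endpoint. For recovery, use a Cox model stratified by PaO2/FiO2 ≤100 v >100, except when PaO2/FiO2 is the factor. For Day 60 mortality, use a logistic interaction or a homogeneity test, and name the scale, because SAP 8.5.1 summarises mortality as a difference in proportions and a logistic interaction works on odds ratios.
- **Remdesivir, dexamethasone, their combination, convalescent plasma:** limit any interaction test to use at randomization (yes or no). Keep categories started after randomization descriptive only.
- **Reporting:** give level-specific estimates with 95% confidence intervals, and state that within-level p-values are not to be compared.
- **Status:** label all of it exploratory and unadjusted for multiplicity, with a 5% false-flag rate per test and a higher rate across 10 or more tests.

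The cost is a few lines of SAP text and one model term per factor, with no new data and no change to the primary analysis. The drawback is low power, about 37% even for true ratios of 1.49 and 1.00 at an even split with 264 events. The SAP should say that a non-significant interaction is inconclusive and does not show that the effect is uniform.
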